## 8.10 Collapsed AEs and Exposure-Adjusted Incidence Rates

In order to account for AEs with multiple occurrences in the same subject, AE records are collapsed for each subject and preferred term when:

- Records have the same onset date.
- The onset date of an event record is either the same day or 1 day later than the resolution date of a preceding event record (contiguous events).
- The onset date of an event record is after the onset date and prior to or on the resolution date of a preceding event record (overlapping events).

The collapsed record contains the earliest onset date (and time, if collected); latest resolution date (and time, if collected); highest intensity in the following order (highest to lowest: very severe, severe, moderate, or mild); AE type of SAE, if ever reported as a SAE, AE otherwise; latest causality, as determined by the last modification time stamp (highest causality in the following order [highest to lowest: related, not related], if records contain the same last modification time stamp with different causalities); treatment required of yes, if ever required; highest action taken in the following order (highest to lowest: drug discontinued, drug interrupted, dose reduced, dose increased, none); latest reported term, as determined by the last modification timestamp.

Incidence rates per 100 person-years of exposure (IR/100 P-Y) are defined as event count \* 100 / person-years of exposure (see [Section 7.6.5](#)). Exposure is defined as time on study therapy (see [Section 7.4.1](#)), plus 5 days for subjects who discontinued study therapy to account for on-treatment safety reporting.

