7.3.3 Nonserious Adverse Events

The collection of nonserious AE information should begin at initiation of study drug. Nonserious AE information should also be collected from the start of a placebo lead-in period or other observational period intended to establish a baseline status for the subjects. During the long-term follow up phase, Adverse Events related to the administration or discontinuation of study drug should be documented for subjects that are not receiving commercially available anti-HBV therapy. Also during the LTFU phase, all adverse events should be documented in subjects receiving rescue open-label ETV.

If an ongoing nonserious AE worsens in its intensity or its relationship to the study drug changes, a new nonserious AE entry for the event should be completed. Nonserious AEs should be followed to resolution or stabilization, or reported as SAEs if they become serious (see Section 7.3.1). Follow-up is also required for nonserious AEs that cause interruption or discontinuation of study drug, or those that are present at the end of study treatment as appropriate.

All identified nonserious AEs must be recorded and described on the appropriate nonserious AE page of the CRF (paper or electronic).

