## **7.6 Safety**

The investigators determine the intensity of AEs and the relationship of AEs to study therapy. The investigators' terms are coded and grouped by system organ class using the latest version of the Medical Dictionary for Regulatory Activities (MedDRA) in production at BMS.

In order to account for AEs with multiple occurrences in the same subject, AE records are collapsed for each subject and preferred term when records have the same onset date, or when records are contiguous or overlapping (see [Section 8.10](#)). All AE presentations are based on collapsed records.

AEs are presented by system organ class and preferred term, both in descending order of incidence on ETV, unless specified otherwise.

AE presentations include both non-serious and SAEs as defined in the protocol, unless specified otherwise. If a subject had an AE with different intensities during the study period, then only the greatest intensity is reported.

On-treatment safety is assessed for the following 3 cohorts (see [Sections 6.1](#) and [6.3](#)):

- Through Week 48 on blinded therapy for treated subjects
  - ETV and PBO are assessed on treatment up to the Week 48 cut, ie, the earlier of (a) 54 weeks, the upper bound of the Week 48 visit window (see [Section 8.4](#)), and (b) the first dose of open-label ETV.
- After Week 48 on blinded therapy or on open-label ETV through Week 96 for the Year 2 Safety Cohort

- ETV, PBO BL and PBO OL are assessed on treatment after the Week 48 cut and up to 102 weeks, the upper bound of the Week 96 visit window (see [Section 8.4](#)).
- On ETV treatment for All ETV Safety Cohort

Note that AEs with onset on the first day of study therapy are considered on treatment, AEs with onset on the first day of ETV are considered on ETV treatment and AEs with onset on the first day of open-label ETV are considered on open-label ETV.

Follow-up safety is assessed for the following 3 cohorts (see [Sections 6.1](#) and [6.3](#)):

- During off-treatment follow-up for off-treatment follow-up subjects in the Post-Year 1 Safety Cohort
- During long-term follow-up for long-term follow-up subjects in the Post-Year 1 Safety Cohort.
- During alternative ETV follow-up for alternative ETV follow-up subjects in the Post-Year 1 Safety Cohort (select endpoints only).

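### The AE collapsing rule ignores study-period boundaries, so an event that becomes severe or serious after a boundary is tabulated in the period where it began and is missing from the period where it worsened

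*SAP*

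**What the plan says.** Protocol 7.3.3 separates a worsening from the event it grew out of: "If an ongoing nonserious AE worsens in its intensity or its relationship to the study drug changes, a new nonserious AE entry" is to be completed, and an event that becomes serious is reported as an SAE.

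SAP 8.10 then joins such entries again: "AE records are collapsed for each subject and preferred term when" they share an onset date, touch (the later one starts on the day the earlier one resolves, or the day after) or overlap. The key is subject and preferred term; study period is not part of it. For the merged record the rule reads "The collapsed record contains the earliest onset date (and time, if collected); latest resolution date (and time, if collected); highest intensity". Seriousness is "AE type of SAE, if ever reported as a SAE, AE otherwise", and the action field takes the "highest action taken in the following order (highest to lowest: drug discontinued, drug interrupted" and so on down the list.

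SAP 7.6 states "All AE presentations are based on collapsed records" and lets onset decide the period, for example "AEs with onset on the first day of ETV are considered on ETV treatment". It says the same for the first day of study therapy and of open-label ETV. The period limits are in SAP 6.1 (on-treatment ends at last dose + 5 days; off-treatment follow-up starts the next day). The Week 48 cut is in SAP 7.6: the earlier of 54 weeks and the first open-label ETV dose.

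**The concern.** The entry that documents a worsening has a correct date when the site records it. The merge discards that date but keeps the grade, the seriousness and the action taken, and attaches them to the date of the milder beginning. If a period boundary lies between the two dates, the harm is credited to the wrong period and leaves no trace in the right one.

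The tables at stake are those for clinical AEs, SAEs and AEs leading to discontinuation, and the exposure-adjusted rates, in three settings: blinded therapy to Week 48, ETV treatment (PBO OL and All ETV), and follow-up after treatment. Serious and severe events are likely to be few in a trial of about 180 children, so one misplaced event can be visible.

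**Working it through.** **Does anything stop the merge at a boundary?** SAP 6.1 defines the periods and says nothing about records that span them. SAP 7.6 assigns collapsed AEs by onset. SAP 8.10 sets no limit by period. SAP 8.4 does select values within a study period first, but only for longitudinal presentations, not for AEs.

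**The rule applied to hypothetical records.** Open-label ETV starts on day 365 and the last dose is on day 1037, so off-treatment follow-up starts on day 1037 + 6 = 1043.

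| Case | Entries as recorded | Under SAP 8.10 and 7.6 | If collapsed within period |
|---|---|---|---|
| A | Grade 1 AE, days 350–371; Grade 3 SAE from day 372 | One Grade 3 SAE, onset day 350: blinded placebo only; absent from PBO OL and All ETV | Grade 1 AE on placebo and Grade 3 SAE on ETV |
| B | Grade 1 AE, days 1030–1049; Grade 4 SAE from day 1050 | One Grade 4 SAE, onset day 1030: on ETV only; absent from off-treatment follow-up | Grade 1 AE on ETV and Grade 4 SAE off treatment |
| C | As A, but the first entry resolves on day 370 | Not merged (the next onset is 2 days later); placed correctly | Same |

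Case C shows the limit: a gap of two or more days from resolution to the next onset, or a different preferred term, escapes the merge. A continuing event that worsens does not.

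**Direction.**
- Placebo-to-ETV switch (case A): a harm leaves the ETV tables and enters placebo, so harm on ETV is understated.
- End of dosing (case B): a harm leaves follow-up and enters the on-ETV tables, so on-ETV harm is overstated and post-treatment harm understated.
- Week 48 cut: SAP 7.6 applies it to both arms. With the plan's 10% dropout per year, 120 × 0.9 = 108 ETV and 60 × 0.9 = 54 placebo subjects cross it. If a fraction f in each arm has an event that worsens across the cut, the inflation is 108f/120 = 0.9f and 54f/60 = 0.9f, the same in both arms.

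**Size of one event.** The plan states no figure for this rule. Inputs are 60 placebo subjects (protocol synopsis), and 10% dropout and 10% placebo seroconversion (protocol 8.1). The plan's own chain reproduces: 20 × 0.9 = 18; 18 × 0.9 = 16.2, given as 16; 16 × 0.9 = 14.4, given as 14.
- Switchers among 60: 60 × 0.9 × 0.9 = 48.6, about 49.
- One event added to placebo: 1/60 = 1.7 percentage points.
- One event removed from PBO OL: 1/48.6 = 2.1 percentage points.
- Rate, assuming 48 weeks on blinded placebo for each subject: 60 × 48/52.18 = 55.2 person-years, so one event is 100/55.2 = 1.8 per 100 person-years.
- One to three shifted events would give +1.7 to +5.0 points on placebo and −2.1 to −6.2 points on PBO OL. This range illustrates scale; it does not predict a count.

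**The case against.** The best defence is that the SAP never states the order of the two steps, and that SAP 7.6 refers to intensities within the study period, which could mean within-period handling. That sentence governs which intensity is reported; it does not say how records merge or which onset they take. The plain reading of 8.10 with 7.6 is merge first, then assign by onset. If the intention was otherwise, one sentence would settle it.

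Much of the rest of the defence stands:
- A reader might infer that the blinded Week 48 comparison is biased against placebo. The documents do not support this: the cut applies to both arms, and nothing in them suggests that events worsen across it more often in one arm.
- A reader might infer that the rule always flatters ETV. At end of dosing it does the reverse for the on-ETV tables.
- A reader might infer that post-treatment exacerbation, a risk named in protocol 1.5, is hidden. SAP 7.6.6.1 measures ALT flares from laboratory data, which collapsing does not touch. Laboratory abnormalities and deaths are also unaffected. HBV progression and malignant neoplasms are tabulated over on-treatment and long-term follow-up together, so they are not lost at end of dosing.
- Not every worsened event reaches a sparse table: an unrelated Grade 1 event that becomes Grade 2 enters neither the Grade 3–4, the SAE nor the related-AE table.
- After treatment, nonserious AEs are collected only in part (protocol 6.3.2 and 7.3.3), which reduces the number that can be misplaced there.
- Alternative-ETV follow-up lies within long-term follow-up. An event that starts off treatment and worsens on alternative ETV is missing from the former table but stays in the latter.
- Collapsed causality follows the latest assessment, with ties going to related. This looks out of step with the worst-case fields, but it is a defensible choice and needs no change.

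**Conclusion.** The concern holds for clinical AE, SAE and discontinuation tables. Followed as written, SAP 8.10 and 7.6 place a worsened event in the period of its mild beginning, and it is missing from PBO OL and All ETV after the switch, or from off-treatment follow-up after dosing ends. The direction depends on the boundary, and no net bias for or against ETV can be claimed.

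How many events are affected cannot be derived: the documents do not say how often an AE is ongoing at a boundary or then worsens. The per-event figures rest on 60 placebo subjects and the plan's dropout and seroconversion assumptions; the rate also assumes 48 weeks of placebo each.

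The SAP should be changed because its AE rule is out of line with its own laboratory rule. SAP 7.6.6.1 defines an emergent abnormality as a grade above the reference, using ETV baseline during open-label ETV for placebo subjects and the EOD grade in follow-up. A laboratory worsening is thus credited to the period in which it happens; a clinical one is not.

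**What to change.** In SAP 8.10, collapse AE records only within a study period. The boundaries are the first dose of study therapy, the Week 48 cut or first open-label ETV dose, last dose + 5 days, and the start of alternative ETV. Count an entry that starts after a boundary as emergent in the later period, with its own intensity and seriousness, only if its intensity is higher than before the boundary or it is newly serious. An entry opened only because the relationship to study drug changed does not count as a new event. Leave the causality rule as it is.

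The cost is SAP wording and a programming change, with no new data. The downside is that one prolonged event can appear in two periods, which a table footnote should state.

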7.3.1 Serious Adverse Events

Following the subject's written consent to participate in the study, all SAEs must be collected, including those thought to be associated with protocol-specified procedures. All SAEs must be collected that occur within 30 days of discontinuation of dosing or within 30 days of the last visit for screen failures. If applicable, SAEs must be collected that relate to any later protocol-specified procedure (eg, a follow-up skin biopsy).

The investigator should notify BMS of any SAE occurring after these time periods that is believed to be related to study drug or protocol-specified procedure.

Serious Adverse Events should be reported during the long-term follow up phase, regardless of whether or not the subjects are receiving commercially available anti-HBV therapy. Any medical event that the investigator considers to be "medically important" in the context of pediatric drug exposure (for example neurodevelopmental delay), may be reported as an SAE under the category "Important Medical Event." (see Section 7.1.1)

Serious adverse events, whether related or unrelated to study drug, must be recorded on the SAE page of the CRF and reported within 24 hours to BMS (or designee) to comply with regulatory requirements. An SAE report should be completed for any event where doubt exists regarding its status of seriousness.

All SAEs must be reported within 24 hours by confirmed facsimile transmission (fax) or scanned and reported via electronic mail. (Note: Follow-up SAE reports should include the same investigator term(s) initially reported.) In selected circumstances, the protocol may specify conditions that require additional telephone reporting. The SAE electronic CRF in the electronic data capture tool should not be used.

If the investigator believes that an SAE is not related to study drug, but is potentially related to the conditions of the study (such as withdrawal of previous therapy, or a complication of a study procedure), the relationship should be specified in the narrative section of the SAE page of the CRF.

If an ongoing SAE changes in its intensity or relationship to study drug, a follow-up SAE report should be sent within 24 hours to the sponsor. As follow-up information becomes available it should be sent within 24 hours using the same procedure used for transmitting the initial SAE report. All SAEs should be followed to resolution or stabilization.

SAE FACSIMILE TRANSMISSION:

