### 8.3 Partial or Missing Safety Information

A missing AE intensity is not imputed. AEs with missing intensity are included in the AE tables for All Grades. AEs with missing relationship are included in tables of “related” AEs.

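### SAP 8.10 sets a merged adverse event's causality by which record was edited last, so an edit unrelated to causality can move the event into or out of the related-event tables

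*SAP*

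**What the plan says.** SAP 8.10 merges records of the same preferred term in one subject when they share an onset date, are contiguous or overlap. It then sets each attribute of the merged record:

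- Intensity and action taken: the highest value. Treatment required: yes if ever required.
- Seriousness: "AE type of SAE, if ever reported as a SAE, AE otherwise".
- Causality: the "latest causality, as determined by the last modification time stamp". The ordering that puts related above not related is used only "if records contain the same last modification time stamp with different causalities".
- Reported term: also from the record modified last.

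SAP 7.6 gives the rule its reach: "All AE presentations are based on collapsed records".

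Two further passages matter. Protocol 7.3.3 states: "If an ongoing nonserious AE worsens in its intensity or its relationship to the study drug changes, a new nonserious AE entry" is to be completed for the event. On missing data, SAP 8.3 states that "AEs with missing relationship are included in tables of" related events, and SAP 7.6.5 repeats this.

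**The concern.** A modification stamp records when a database entry was last touched. That may be when the investigator revised the causality, but it may equally be when a date, a spelling or a query was settled. Protocol 9.1.3 says that corrections to electronic CRFs generate a dated audit trail, so edits that have nothing to do with causality are time-stamped too. The tie wording in SAP 8.10 speaks of records containing a stamp, which points to one stamp per record and not one per causality field. Nothing in the SAP links it to the date of the judgement.

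If the records being merged disagree, the related-event tables then depend partly on the order of data cleaning. SAP 9 presents the All ETV Safety Cohort at more than one analysis, so an event's label could also differ between reports with no change in its clinical content. What is at stake is the reproducibility of the drug-related tables in a paediatric safety database. The occurrence, grade and seriousness of events are not in question.

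**Working it through.** The plan gives no figure to reproduce here. The check applies the written rule to every two-record case.

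**Do discordant merges arise?** Under protocol 7.3.3, a worsening or a changed relationship produces a second entry for an ongoing event. If the preferred term is the same, that entry normally overlaps or adjoins the first, and SAP 8.10 merges such entries. So discordant pairs follow from the reporting rules.

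**What does the rule return?** Let R be related and N not related. Record 1 holds the earlier judgement and record 2 the later one. There are 4 causality pairs and 3 stamp orders (record 2 later, record 1 later, equal), so 4 × 3 = 12 cases. In the 6 concordant cases the rule makes no difference. The 6 discordant cases are:

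| Record 1 → record 2 | Later stamp | SAP 8.10 | Any record related | Record 2 (later judgement) |
|---|---|---|---|---|
| R → N | record 2 | N | R | N |
| R → N | record 1 | R | R | N |
| R → N | equal | R | R | N |
| N → R | record 2 | R | R | R |
| N → R | record 1 | N | R | R |
| N → R | equal | R | R | R |

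Three things follow.

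1. With the clinical content fixed, reversing the stamp order reverses the label (rows 1 and 2; rows 4 and 5).
2. Judged by whether any record was related, SAP 8.10 returns related in 4 of 6 cases and not related in 2 of 6 (rows 1 and 5).
3. Judged by the investigator's later view, row 1 is correct. An edit to the older record gives an error in each direction: row 2 keeps an attribution that was withdrawn, and row 5 drops one that was added. Row 3 also keeps a withdrawn attribution, through the tie-break.

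These are enumerated cases. The rows are not equally likely, so the counts do not estimate a rate.

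**Which outputs use the field?**

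- Affected: the all-grade related and Grade 2 to 4 related tables (SAP 7.6.5); the Grade 2 to 4 related summaries by subgroup (7.6.8); related SAEs leading to death, and the counts and exposure-adjusted rates of related SAEs (7.6.2).
- Not affected: all-causality AEs, Grade 3 to 4 AEs, all SAEs, deaths, discontinuations due to AEs, and the exposure-adjusted rates in 7.6.5, which are not restricted to related events. Under protocol 7.3.1, SAEs go to the sponsor within 24 hours whether related or not, and that process does not use the merge rule.

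**Missing relationship.** SAP 7.6.5 and 8.3 count a missing relationship as related. SAP 8.10 does not say what happens when such a record is merged. Read literally, a later-stamped N record makes the merged event N, so the convention no longer operates for that event.

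**The case against.** The strongest reply is that taking the latest causality is a sound aim. SAP 7.6 leaves relationship to the investigator. A change of view produces a new entry (protocol 7.3.3) or a follow-up SAE report (7.3.1), so the newer record will normally carry both the current judgement and the later stamp. The reported term is handled in the same way, so causality is not a lone exception to a worst-case scheme. An any-record-related rule would also override an investigator who withdrew an attribution for good reason. Combined with the highest-intensity rule, it can create a Grade 2 related event from a Grade 1 related record and a Grade 2 unrelated one. All of this stands. It leaves one weakness: the edit stamp is a poor proxy for the latest judgement once an older record is touched again. The mixed pairing of grade and causality is also possible under the present rule.

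A reader might infer more than the documents support:

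- *That related events are lost in one direction.* The table shows errors both ways.
- *That about half of discordant events lose the related label.* This needs edit order to be independent of causality, whereas the protocol creates discordant records in time order. No discordance rate is given either, so no percentage loss can be derived.
- *That separate SAE handling makes the stamps unreliable.* Protocol 7.3.1 does say of SAEs: "The SAE electronic CRF in the electronic data capture tool should not be used". But no passage says how stamps are generated or reconciled across the two routes.
- *That SAP 8.3 contradicts 8.10.* SAP 8.3 concerns missing relationships, not two recorded judgements that differ.

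**Conclusion.** The point holds as a minor one. As written, the causality of a merged event with discordant records depends on edit order, and an edit unrelated to causality can move it into or out of the related tables listed above. This rests on reading the stamp as record-level, which the tie wording suggests but the SAP does not state. If the stamp belonged to the causality field alone, the data-cleaning route would largely close. The direction of error is not fixed, and its frequency cannot be estimated from the documents. Through Week 48 the same rule applies to both blinded arms, and the all-causality comparison is untouched. The case for changing it is that the output should depend on clinical content, and the change is cheap.

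**What to change.** In SAP 8.10, stop using the modification stamp for causality. Replace the rule with: *a merged event is related if any component record is related or has a missing relationship; otherwise it is not related.* This extends the SAP's own tie-break and its missing-relationship convention. Add a listing of merged events whose components disagree, showing each record's grade, dates and causality, so that later reassessments remain visible.

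If the sponsor prefers the investigator's latest judgement, define latest by the date of the causality assessment or by the clinical sequence of the records (onset date), keep related as the tie-break, and state how a missing relationship is treated. Onset is among the items that protocol 7.3 requires for every AE. An assessment date is not on that list, so check that it is collected before relying on it.

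The cost is one line of SAP text, a small programming change and a listing. Under the first option, related counts may be slightly higher, and a merged event may pair the highest grade with relatedness from a milder record, which the current rule can also do.
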